12. STATISTICAL CONSIDERATIONS

12.1. Analysis Datasets

This study will identify the following datasets:

- Intent to treat dataset: All patients who have enrolled in the study
- Safety dataset: All patients who receive at least 1 dose of VRx-3996.
- Efficacy dataset: All patients with measurable disease at Screening who have met all inclusion criteria and have received at least 1 post-baseline tumor assessment for efficacy.

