3.4.2.2 Secondary Efficacy Variables

Secondary efficacy endpoints include the following:

- Duration of response: defined as the interval from date of first observed complete or partial response per Lugano criteria ([Cheson 2014](#)) to the date of documented disease progression or death due to any cause. Dates of progression and censoring will be determined as described in [Section 4.4.6.2](#).
- Disease control rate: defined as the proportion of patients with CRs, PRs, or stable disease (SD) per Lugano criteria ([Cheson 2014](#)).
- Time to response: defined as the interval from the start of study drug treatment to the first documentation of CR or PR per Lugano criteria ([Cheson 2014](#)). Patients who do not achieve a response will be censored at the date of their last tumor assessment.
- Progression-free survival: defined as the interval from the start of study treatment to the first documented date of disease progression or death from any cause, whichever occurs first. Dates of progression and censoring will be determined as described in [Section 4.4.6.2](#).

- Overall survival: defined as the time from date of first study drug treatment to date of death, for any reason. Patients without documentation of death at the time of analysis will be censored at the date the patient was last known to be alive.

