4.2 Analysis Sets

The analysis sets are defined as follows:

- Intent-to-Treat (ITT) Set: The ITT includes all enrolled patients.
- Safety Analysis Set: includes all enrolled patients who receive at least one dose of nanatinostat.
- Efficacy Evaluable Set: includes all patients with measurable/evaluable disease at screening who have met all eligibility criteria and have at least one evaluable post-baseline efficacy tumor assessment.
- Pharmacokinetic Analysis Set: includes all patients in the ITT who have received at least one post-dose PK sample obtained and analyzed (i.e. valid result being

available). The PK Analysis Set is used for tabulation of nanatinostat and ganciclovir concentrations from PK plasma samples.

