4.6 Efficacy Evaluation

4.6.1 Datasets Analyzed

All efficacy summaries will be based on the EES. A data listing of patients excluded from the EES, to include the reason for exclusion, will be presented.

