4.6.3 Secondary Endpoint Analysis Methods

Disease control rate will be analyzed using the same statistical methodologies as applied to the primary efficacy endpoint in [Section 4.6.2](#).

Time to response, DoR, PFS, and OS will be summarized in days using Kaplan-Meier (KM) methodology. The number of patients who experienced the event of interest and the number of patients censored will be presented; as will KM product limit estimates of the median with associated CIs (where estimable) using Greenwood's formula. The range for all patients, as well as those who experience the event of interest will also be summarized. Kaplan-Meier estimates of the survival distribution function for DoR, PFS, and OS over time will be generated for all patients receiving study treatment. All derived efficacy measures will also be provided in a separate listing. A swimmer plot of each patient's overall tumor response assessment by EBV+ lymphoma subtype will also be presented. A listing will be provided that lists each patient's lymphoma subtype, response category, and percentage of EBER-ISH positive tumor cells.

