4.6.5.2 Handling of Dropouts or Missing Data

Best overall response is based on those patients with available data (baseline and post-baseline response assessment). Non-evaluable patients are considered non-responders and will be included in the denominator. Progression-free survival and DoR will be right-censored for patients who met one of the following conditions: 1) non-protocol systemic anti-cancer treatment started before documentation of disease progression or death, 2) death or disease progression after more than one missed disease assessment visit, or 3) alive and does not have documentation of disease progression before a data analysis cutoff date. These conventions are based on the FDA Guidance for Industry, *Clinical Trial Endpoints for the Approval of Cancer Drugs and Biologics* (2018). The analysis of PFS and DoR will be right-censored according to the conventions described in [Table 4](#).

Table 4 Conventions for Censoring for PFS and DoR

Situation	Date of Progression or Censoring	Outcome
New anti-cancer therapy started before documentation of PD or death	Date of last disease assessment prior to start of new anti-cancer therapy	Censored
Death or PD immediately after more than one consecutively missed disease assessment visit	Date of last disease assessment visit without documentation of PD that is before the first missed visit	Censored
Alive and without PD documentation	Date of last disease assessment	Censored
Death or PD between planned disease assessments	Date of death or first disease assessment showing PD, whichever occurs first	Progressed
Death before first disease assessment	Date of death	Progressed

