4.6.5.6 Use of an “Efficacy Subset” of Patients

The efficacy analysis will be performed on the Efficacy Evaluable Set, which is a subset of the ITT Set.

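### The SAP contradicts itself on the population for PFS and OS; if the Efficacy Evaluable Set governs, patients who die before any tumour assessment drop out and the medians are too long

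*SAP*

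**What the plan says.** Two parts of the SAP point to the Efficacy Evaluable Set (EES).

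- Section 4.6.1: "All efficacy summaries will be based on the EES".
- Section 4.6.5.6: "The efficacy analysis will be performed on the Efficacy Evaluable Set, which is a subset of the ITT Set".

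PFS and OS fall under these sentences because section 3.4.2.2 lists both under the words "Secondary efficacy endpoints include the following". Under section 4.2, members of the EES must have measurable or evaluable disease at screening, meet all eligibility criteria, and "have at least one evaluable post-baseline efficacy tumor assessment".

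Two other parts point to all treated patients.

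- Section 4.6.3: "Kaplan-Meier estimates of the survival distribution function for DoR, PFS, and OS over time will be generated for all patients receiving study treatment".
- Section 4.6.5.2, Table 4, has a row headed "Death before first disease assessment". It is scored as an event on the date of death.

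The sentences in 4.6.3 on event counts, censoring, medians and confidence intervals name no set.

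Both clocks start at first treatment. PFS, for example, is "defined as the interval from the start of study treatment to the first documented date of disease progression or death from any cause" (SAP 3.4.2.2). The protocol does not settle the matter. Its section 12.1 defines an efficacy dataset of patients who, among other conditions, "have received at least 1 post-baseline tumor assessment for efficacy", but section 12.4.2 assigns no dataset to PFS or OS.

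**The concern.** Membership of the EES depends on something that happens after time zero. A patient has to stay alive and in the study long enough to be assessed, while survival time is counted from the first dose. Someone who dies unassessed contributes neither an event nor time at risk. The remaining patients could not have died before their assessment, so the early part of their follow-up is immortal time and the estimated median moves upward.

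This matters here for three reasons. Early death is plausible on the documents' own account: the protocol describes the likely outcome as fatal (section 18.1) and admits patients with ECOG status 2 (section 4.1). The study has one arm, so no control group carries the same selection, and the absolute median is what readers will take away. The trial is also open-label, so an unresolved choice of population can be made after the outcomes are known. The SAP's introduction says it was written to avoid such choices.

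The response-rate denominator is a separate question and is not argued here.

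**Working it through.** **Figures in the plan.** The documents give no PFS or OS median and no early death rate, so there is no figure to reproduce. The medians below are assumptions.

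**Step 1: can the texts be reconciled?** Every member of the EES has a post-baseline assessment, so none can have died before the first one. The Table 4 row is therefore empty if the EES is the population. The table serves PFS and duration of response. A patient who was never assessed cannot be a responder, so the row has meaning only for PFS, and only in a population wider than the EES. The all-treated sentence in 4.6.3 likewise cannot hold together with a rule that every efficacy summary uses the EES.

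**Step 2: inputs for the size.**

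- Cycle length is 28 days (SAP 3.1), and the first scheduled assessment follows Cycle 2 (Protocol section 7; SAP 3.1). So tau = 2 × 28 = 56 days.
- SAP 4.1.5 divides days by 30.44 to get months: 56 / 30.44 = 1.84 months.
- Assumed: true median m, hazard shape, and the share u of events before tau in patients with no evaluable assessment.

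**Step 3: formula.** Let S be the true survival function and F = 1 − S(tau). A fraction u × F of patients is removed. After tau, the proportion of the EES still event-free is S(t) / (1 − uF). The EES median therefore solves S(t) = 0.5 × (1 − uF).

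**Step 4: OS, constant hazard, u = 1.** With S(t) = 2^(−t/m), the solution is t = m + tau, a shift of 1.84 months whatever m is. For m = 6: F = 1 − 2^(−1.84/6) = 0.191; 0.5 × 0.809 = 0.404; t = 7.84.

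| True OS median (months) | Removed | Of 30 patients | EES median (months) |
|---|---|---|---|
| 3 | 35% | about 10 | 4.84 |
| 6 | 19% | about 6 | 7.84 |
| 9 | 13% | about 4 | 10.84 |
| 12 | 10% | about 3 | 13.84 |

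**Step 5: OS, other hazard shapes, u = 1.** Weibull with shape k: S(t) = exp(−ln 2 × (t/m)^k).

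| Shape k | m = 3 | m = 6 | m = 12 |
|---|---|---|---|
| 1.5 (hazard rises) | 3.90 | 6.66 | 12.48 |
| 1.0 | 4.84 | 7.84 | 13.84 |
| 0.7 (hazard falls) | 6.46 | 10.07 | 16.87 |

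**Step 6: PFS, constant hazard.** An early progression documented at an evaluable assessment keeps the patient in the EES, so u may be well below 1.

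- u = 0.25, m = 6: 0.5 × (1 − 0.25 × 0.191) = 0.476, so t = 6.42.
- u = 0.5, m = 6: 0.5 × (1 − 0.5 × 0.191) = 0.452, so t = 6.87.
- u = 1, m = 6: t = 7.84.
- m = 3: about 3.4 at u = 0.25, rising to 4.84 at u = 1.

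The shift is upward in every case. Patients who leave alive without an assessment are also outside the EES; their effect is not sized here.

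**The case against.** The strongest reply is that the specific text should override the general. Section 4.6.3 and Table 4 deal with these endpoints by name, and both keep early deaths in. A Kaplan-Meier median is normally read off the same estimate as its curve, so the all-treated sentence may be meant to cover the medians too. A reader might infer that early deaths are definitely deleted, or that the reported median and the plotted curve come from different populations. The documents do not establish either. The median sentence names no set, and the all-treated wording could even mean only that cohorts are pooled. What stands is that 4.6.1 and 4.6.5.6 say the opposite without exception.

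A second reply is that the EES does not require a week-8 scan. It requires an evaluable assessment. Response assessment combines physical examination and imaging (Protocol section 10), the schedule of events also has a disease assessment at End of Treatment, and the timing may be adjusted. This is correct. Only patients with no evaluable assessment at all are lost, so u = 1 is an upper case.

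A third reply is that these are secondary endpoints in a descriptive study with no hypothesis testing, and that no stopping or dose rule uses them. The plan also lists patients excluded from the EES with reasons (4.6.1), all deaths (4.5.3) and derived efficacy measures (4.6.3). This lowers the seriousness. The listings would let a careful reader find the missing deaths, but they would not correct the printed median.

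**Conclusion.** The contradiction is real and should be fixed, though it is not a critical flaw. Sections 4.6.1 and 4.6.5.6 cannot both stand beside section 4.6.3 and Table 4. The upward bias is conditional: it arises if the EES is applied to the event counts, medians and intervals, and in that case the medians may also disagree with the curves.

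The direction is firm but the size is not. The +1.84 months for OS requires a constant hazard and every death before day 56 unassessed. At an assumed true median of 6.0 months, the two other hazard shapes move the result to 6.7 or 10.1. For PFS, the 6.4 months holds only if a quarter of early events are unassessed.

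Replacement could add to the selection. Protocol 3.18 and SAP 3.1.2 allow Phase 2 patients without a disease assessment to be replaced, and neither says whether replaced patients stay in the survival analyses.

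**What to change.** - In SAP 4.6.1 and 4.6.5.6, state that event counts, medians, confidence intervals and curves for PFS and OS are all analysed from first dose in the Safety Analysis Set, meaning all treated patients including any who are replaced.
- State that the Table 4 row for death before the first assessment applies in that analysis.
- Align 4.6.3 by naming the same set in the sentences on counts and medians.
- If an EES version is shown, label it a sensitivity analysis.

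The cost is a few lines of SAP text, with no new data collection. The reported medians may be somewhat less favourable.

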4.6.2 Primary Efficacy Endpoint Analysis Methods

Counts and percentages for each tumor response category per investigator assessment will be presented by study phase and cohort. This analysis will also be presented by lymphoma subtype. The best overall response, as well as the ORR with corresponding exact binomial 95% confidence interval using the Clopper-Pearson Method, will also be presented.

Results from tumor assessments will be provided in separate listings.

4.6.3 Secondary Endpoint Analysis Methods

Disease control rate will be analyzed using the same statistical methodologies as applied to the primary efficacy endpoint in [Section 4.6.2](#).

Time to response, DoR, PFS, and OS will be summarized in days using Kaplan-Meier (KM) methodology. The number of patients who experienced the event of interest and the number of patients censored will be presented; as will KM product limit estimates of the median with associated CIs (where estimable) using Greenwood's formula. The range for all patients, as well as those who experience the event of interest will also be summarized. Kaplan-Meier estimates of the survival distribution function for DoR, PFS, and OS over time will be generated for all patients receiving study treatment. All derived efficacy measures will also be provided in a separate listing. A swimmer plot of each patient's overall tumor response assessment by EBV+ lymphoma subtype will also be presented. A listing will be provided that lists each patient's lymphoma subtype, response category, and percentage of EBER-ISH positive tumor cells.

4.6.4 Exploratory Endpoint Analysis Methods

Each patient's EBV viral load will be plotted over time by lymphoma subtype and displayed on logarithmic scales.

4.6.5 Statistical/Analytical Issues

4.6.5.1 Adjustments for Covariates

There are no planned applications of covariate adjustments; all statistical results are descriptive in nature.

4.6.5.2 Handling of Dropouts or Missing Data

Best overall response is based on those patients with available data (baseline and post-baseline response assessment). Non-evaluable patients are considered non-responders and will be included in the denominator. Progression-free survival and DoR will be right-censored for patients who met one of the following conditions: 1) non-protocol systemic anti-cancer treatment started before documentation of disease progression or death, 2) death or disease progression after more than one missed disease assessment visit, or 3) alive and does not have documentation of disease progression before a data analysis cutoff date. These conventions are based on the FDA Guidance for Industry, *Clinical Trial Endpoints for the Approval of Cancer Drugs and Biologics* (2018). The analysis of PFS and DoR will be right-censored according to the conventions described in [Table 4](#).

Table 4 Conventions for Censoring for PFS and DoR

Situation	Date of Progression or Censoring	Outcome
New anti-cancer therapy started before documentation of PD or death	Date of last disease assessment prior to start of new anti-cancer therapy	Censored
Death or PD immediately after more than one consecutively missed disease assessment visit	Date of last disease assessment visit without documentation of PD that is before the first missed visit	Censored
Alive and without PD documentation	Date of last disease assessment	Censored
Death or PD between planned disease assessments	Date of death or first disease assessment showing PD, whichever occurs first	Progressed
Death before first disease assessment	Date of death	Progressed

4.6.5.3 Interim Analyses and Data Monitoring

An SRC will govern the conduct of the study. The SRC will consist of the following individuals appointed by Viracta:

- Study Investigators
- Study Medical Monitor
- A Viracta Representative

Responsibilities of the SRC will include the following:

- Reviewing study safety data throughout conduct of the study
- Confirming or modifying the specific dose escalations between cohorts
- Defining intermediate dose levels as appropriate
- Declaring the maximum tolerated dose (if reached)
- Determining the RP2D
- Providing guidance on treatment-related issues raised by an Investigator

The SRC will meet at the end of each cohort during the Phase 1b portion and approximately quarterly during the Phase 2 portion, or as needed based on the rate of enrollment. A core SRC consisting of two investigators and one clinical expert appointed by the sponsor will assess the toxicity during Phase 2 dose expansion.

4.6.5.4 Multicenter Studies

This is a multicenter study, with approximately 30 sites expected to participate. Efficacy data collected from all study sites will be pooled for data analysis. The effect of study site on the efficacy analysis results may be explored post-hoc, as needed.

4.6.5.5 Multiple Comparisons/Multiplicity

There will be no adjustments for multiple comparisons in the efficacy analysis for this study. Results are descriptive in nature and no statistical hypothesis testing is planned.

4.6.5.6 Use of an “Efficacy Subset” of Patients

The efficacy analysis will be performed on the Efficacy Evaluable Set, which is a subset of the ITT Set.

4.6.5.7 Active-Control Studies Intended to Show Equivalence

This study does not include an active-control product and is not intended to demonstrate equivalence between any two drug products.

4.6.5.8 Examination of Subgroups

The primary efficacy endpoint will be summarized by various subgroups of interest based on baseline and demographic categories including age (e.g., < 65 years of age and \geq 65 years of age) and number of prior therapies (e.g., \geq 1 prior therapies and \geq 2 prior therapies). Summaries by subgroup will only be produced if there are at least 6 subjects in the category of interest.

Additional subgroup analyses may be performed post-hoc, as appropriate.

4.7 Pharmacokinetics

The PK Analysis Set will be used for individual plasma concentration listings and summaries of plasma concentrations. The PK Population will also be used for individual and mean figures for plasma concentrations.

The PK Analysis Set will be used for noncompartmental analyses (NCA), inferential statistics, PK parameter listings, and parameter summaries.

4.7.1 Data Handling

Plasma concentrations that are below the limit of quantification (BLQ) will be treated as zero for the calculation of descriptive statistics. If the calculated mean concentration is BLQ, the mean value will be reported as BLQ, and the SD and CV% will be reported as not applicable. For PK analysis, all predose BLQ values will be treated as zero and all postdose BLQ values will be treated as missing. If consecutive BLQ concentrations are followed by quantifiable concentrations in the terminal phase, those quantified concentrations after BLQ concentrations will be treated as missing. Missing concentrations will be treated as missing from the PK parameter calculations.

For Cycle 1 Day 1 only, if the pre-dose value is $> 5\%$ of C_{max} , the subject will be flagged in all associated data listings and the affected profile will be excluded from all PK summaries and statistical evaluations.

4.7.2 Plasma Concentrations

The PK sampling schedule with the allowable time window for all patients is displayed in Table 14 in all versions of study protocol. Serial blood samples for the determination of nanatinostat and ganciclovir will be collected on Cycle 1 Day 1 for all patients, and Cycle 2 Day 1 for some patients in Phase 2 capsule cohort and all patients in Phase 2 tablet cohort.

PK collections that have an actual sampling time that is out of time window and deviates by more than 20% of the nominal sampling time will be flagged in the data listings and excluded from the calculation of concentration summary statistics. If an actual blood collection time or a dosing time is missing, the nominal time may be used. Individual plasma concentrations will be presented in data listings and summarized separately using descriptive statistics (number of subjects (N), number of observations (n), arithmetic mean, SD, CV%, median, minimum, and maximum) by nominal time point for each treatment.

Individual plasma concentrations will be plotted by actual time on both linear and semi logarithmic scales. Mean plasma concentrations will be plotted by treatment and nominal time on both linear and semi-logarithmic scales with all treatments overlaid on the same plots.

Plasma PK concentrations will be reported to 3 significant figures in summary statistics except n (and N), and CV%, which will be reported to integer and 1 decimal place, respectively.

4.7.3 Plasma Pharmacokinetic Parameters

Plasma concentration-time data will be analyzed by non-compartmental analysis using Base SAS® software, version 9.4 or higher. The following PK parameters will be calculated for nanatinostat and ganciclovir, where data permit:

Table 5 Pharmacokinetic Parameters

C_{\max}	Maximum observed concentration.
T_{\max}	Time of maximum observed concentration.
T_{last}	Time of last measurable concentration
AUC_{0-t}	Area under the concentration-time curve from time 0 to the last measurable observed concentration (C_t), calculated using the linear trapezoidal rule.
$AUC_{0-\infty}$	Area under the concentration-time curve from time 0 extrapolated to infinity, calculated as $[AUC_{0-t} + (C_{\text{last}} / \lambda_z)]$ where C_{last} is the last observed measurable concentration (for Cycle 1 Day 1 only) (if applicable)
AUC_{0-6h}	Area under the concentration-time curve from time 0 to 6 hours (if applicable for nanatinostat)
AUC_{0-7h}	Area under the concentration-time curve from time 0 to 7 hours (if applicable for ganciclovir)
AUC_{0-8h}	Area under the concentration-time curve from time 0 to 8 hours (if applicable for nanatinostat and ganciclovir)
AUC_{0-24h}	Area under the concentration-time curve from time 0 to 24 hours (if applicable)
λ_z	Apparent terminal elimination rate constant, where λ_z is the magnitude of the slope of the linear regression of the log concentration versus time profile during the terminal phase.
$t_{1/2}$	Apparent terminal elimination half-life, calculated as: $\ln(2) / \lambda_z$.
CL/F	Apparent total body clearance, calculated as: Dose / $AUC_{0-\infty}$ for C1D1, and Dose / AUC_{0-24h} for Cycle 2 Day 1.
V_z/F	Apparent volume of distribution during the terminal phase, calculated as: Dose / $[\lambda_z * AUC_{0-\infty}]$ for C1D1, and Dose / $[\lambda_z * AUC_{0-24h}]$ for Cycle 2 Day 1.
$\%AUC_{\text{ext}}$	Percentage of $AUC_{0-\infty}$ due to extrapolation; $AUC_{0-\infty}$, CL/F and V_z/F values on C1D1 will be flagged and excluded from summary statistics where $\%AUC_{\text{ext}} > 20\%$.
$AR_{C_{\max}}$	Accumulation ratio based on C_{\max} between Cycle 2 Day 1 and Cycle 1 Day 1
$AR_{AUC_{0-24h}}$	Accumulation ratio based on AUC_{0-24h} between Cycle 2 Day 1 and Cycle 1 Day 1

Actual sampling times will be used for the estimation of all plasma PK parameters, and all concentrations will be included in the analysis (including concentrations collected outside predefined collection windows).

Plasma PK parameters will be presented in data listings and summarized separately using descriptive statistics (number of subjects (N), number of observations (n), arithmetic mean, SD, CV%, geometric mean, geometric CV%, median, minimum, and maximum) by treatment. T_{max} will be summarized using number of observations, median, minimum, and maximum only.

Plasma PK parameters will be displayed to 3 significant figures in all data listings and summary tables except for CV%, which will be reported to 1 decimal place. Time variables (t_{max} , λ_z lower, and λ_z upper) will be displayed to 2 decimal places.

